2. PURPOSE

The purpose of this statistical analysis plan (SAP) is to describe the planned analyses and reporting for Part 1 of protocol ADX-102-SLS-006., Final Version 5.0 28 September, 2018.

This SAP is being written with due consideration of the recommendations outlined in the most recent International Council on Harmonization (ICH) E9 Guideline entitled Guidance for Industry: Statistical Principles for Clinical Trials and the most recent ICH E3 Guideline, entitled Guidance for Industry: Structure and Content of Clinical Study Reports (CSR).

This SAP is a summative and definitive plan. It describes the data that will be analyzed and the subject characteristics, efficacy, and safety assessments that will be evaluated. This SAP provides details of the specific statistical methods that will be used. The statistical analysis methods presented in this document will supersede the statistical analysis methods described in the clinical protocol. If additional analyses are required to supplement the planned analyses described in the SAP, they will be labeled as posthoc and will be identified in the CSR.

2.1. **RESPONSIBILITIES**

Syneos Health will perform the statistical analyses described herein and is responsible for the production and quality control (QC) of all tables, figures, and listings associated with these analyses. ECG, Pharmacokinetics (PK) and Pharmacodynamics (PD) analysis will be conducted independently and are outside the scope of this SAP and will be detailed in separate analysis plans.

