8.2. CONTINGENCIES DUE TO LIMITATIONS INHERENT IN SLS RESEARCH

There will be no adjustment for multiplicity in the analyses of primary and secondary endpoints. The limitations of achieving statistical power due to the limited availability of subjects as well as the longevity and consistency of SLS symptoms make statistical significance difficult to achieve.

In this Phase 3 clinical trial, efficacy decisions must rely upon a clearly observable trend in change in skin scaling, a socially stigmatic symptom of great discomfort that absent a novel treatment will require an inordinate amount of attentiveness on a daily basis for the life of the patient. Thus, significance levels are provided in this clinical trial as an additional index of change rather than an inferential expectation.

Syneos Health #1009367

If warranted by observed data characteristics relative to model assumptions, non-parametric methods and small sample statistical methods may be substituted for one or more of the below anticipated model based analyses. The rationale for any such change will be provided.

Finally, if statistical power is materially increased through the addition of one or more continuous or stratification covariates to a statistical model described in this SAP, the model will include the covariate(s). Analogously, if stratification adds power to a non-parametric or small sample procedure, the analysis will include stratification.

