8.3. DATA CONSIDERATIONS

Due to the limited sample size for Part 1 of the clinical trial, descriptive statistics are planned for the primary and secondary endpoints. Inferential statistics will be used for the primary analysis.

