10.1. PRIMARY EFFICACY ENDPOINT AND ANALYSIS

The primary endpoint for the clinical trial is change from baseline in the VIIS scaling score in drug-treated subjects, as assessed by the investigator, in the target efficacy area. The VIIS provides five-point Likert scales (range 0-4) for erythema and scaling that increases in severity with increasing score values.

The target efficacy area for all efficacy analyses will be one of the body sites as defined in the VIIS tool (with the exception of Dorsal foot) with Grade 2 or higher on baseline VIIS scaling score as assessed by the Investigator.

The within-group change from baseline will be the primary focus of interest in the primary analysis.

Syneos Health #1009367

Primary Analysis

A Mixed Model Repeated Measures (MMRM) model will be used to perform the primary analysis of the VIIS scaling score in drug-treated subjects (not vehicle-treated subjects). Change from baseline VIIS scaling score will serve as the dependent variable. The model will include the baseline value (Visit 1) as a covariate (if useful) and visit (treated as a factor; the visit term will cover Visit 1, 5, 7, and 8). An unstructured covariance structure will be assumed and a Type III model will be evaluated. If the unstructured covariance structure matrix results in a lack of convergence, then Toeplitz (TOEP), first-order autoregressive (AR1), compound symmetric (CS) covariance structure will be used in that order. If the MMRM model cannot hit convergence with any correlation structure, then a within-subject t-test (baseline-adjusted, if useful) will be used to compare baseline to Visit 8. It should be noted that improvement will be signified by the existence of a negative change score.

The primary efficacy endpoint will be summarized descriptively by visit and across all visits. The table will contain descriptive statistics on observed values and change from baseline at each time point.

The primary analysis using the MMRM model will be summarized in a consolidated table containing the following:

- Descriptive statistics for change scores at baseline and each post-treatment time point.
- The LS mean change scores with accompanying standard errors and 95% confidence intervals for each visit.
- Within-group contrasts for each given visit.
- Significance levels for the visit effects.

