Along with the table detailing the results of the MMRM model, a consolidated table presenting the essential information for the primary analysis will be constructed. The primary endpoint will be deemed to have been met if the Visit 8 (week 24) term is significant, and the term coefficient is negative.

Secondary and Sensitivity Analyses Related to the Primary Outcome Variable

The following analyses will be performed to provide additional insight into VIIS scaling.

Responder Analysis

For drug-treated subjects, responder status will be assigned to a subject if at a given post treatment time point an improved change from baseline of at least 1 VIIS scaling

Syneos Health #1009367

unit occurs. A Generalized Estimating Equation (GEE) model will be used to evaluate the predicted log odds, odds and probability of response. The model will include the effect of visit (treated as a factor). An unstructured covariance structure will be assumed and a Type III model will be evaluated. If the unstructured covariance structure matrix results in a lack of convergence, then first-order autoregressive (AR1) and compound symmetric (CS) covariance structure will be used in that order.

Results will be captured in a consolidated table that contains the following information:

- Number and percent of observed responders and non-responders at all post-treatment time points;
- Significance levels for the visit effects;
- The model predicted log odds, odds and probability of response with standard errors and 95% confidence intervals for each visit;
- Within-group contrasts expressed as an odds ratio, accompanied by a 95% confidence interval.

AUC Analysis

For drug-treated subjects, AUC for change from baseline over all post-treatment time points will be calculated for each subject using the trapezoidal rule. A linear model comparing AUC to zero (no change from baseline) will be performed.

Survival Analysis

For drug-treated subjects, time to first response (i.e., a one-unit VIIS scaling improvement) will be captured in a Kaplan Meier plot. A hazard rate estimate will be generated.

Analysis for Patients Experiencing one or more Treatment interruptions

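### The Part 1 primary test lets covariates enter when they help, by undefined triggers and for an undefined Visit 8 term, so its false-success rate can exceed that of the unadjusted test.

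*SAP*

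**What the plan says.** SAP 8.2 ends with an operative rule: "if statistical power is materially increased through the addition of one or more continuous or stratification covariates", the model takes them in, and stratification is treated likewise for non-parametric or small-sample procedures. There is no list of candidates, no measure of power, no threshold and no point in time.

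SAP 10.1 fits the primary MMRM to drug-treated subjects only and says: "The model will include the baseline value (Visit 1) as a covariate (if useful"). The fallback repeats the condition: "a within-subject t-test (baseline-adjusted, if useful) will be used to compare baseline to Visit 8". On the visit factor, "the visit term will cover Visit 1, 5, 7, and 8". Success is then read from a p-value and a negative coefficient: "The primary endpoint will be deemed to have been met if the Visit 8 (week 24) term is significant".

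The status of that p-value differs between sections. SAP 8.2 says that "significance levels are provided in this clinical trial as an additional index of change rather than an inferential expectation", while SAP 8.3 says: "Inferential statistics will be used for the primary analysis". SAP 2 states: "This SAP is a summative and definitive plan".

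Protocol 10.4 and the synopsis permit, but do not require, covariates in the one-sample 95% CI to gain power. Their example is a mean-centred covariate.

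**The concern.** A covariate admitted because it sharpens the result is a data-dependent choice of model. The SAP makes it part of a definitive plan, so the resulting p-value would be reported as pre-specified. The primary model contains only the drug arm, so a gain observed in that model can be seen only once the arms are known. Nothing requires the choice to be made before unblinding, and SAP 12 describes the Part 1 analysis as fully unblinded.

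The object of the test is also unclear. Change at Visit 1 is 0 by definition, yet Visit 1 is a level of the visit factor. The Visit 8 term could be the Visit 8 LS mean against 0, a contrast with Visit 1, or a raw coefficient. These respond differently to a covariate.

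At stake is whether Part 1 is labelled as having met its primary endpoint in about 6 treated subjects, and the width of the reported interval.

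**Working it through.** **Inputs.** Drug arm n = 6 (synopsis: 6 treated, 3 control). Protocol 10.1: two-sided one-sample t-test, alpha 0.05, change 0.5, SD 0.6 or 0.7. SAP 10.1 states no alpha for its success rule, so 0.05 two-sided is assumed. Also assumed, because the documents give neither: the number of candidate covariates and R², the share of change variance that a covariate explains. Complete data and a true mean change of 0 are used throughout, except for the power figures in step 1.

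**1. The plan's own figure.** For n = 20 the noncentrality is 0.5√20/0.6 = 3.73 and 0.5√20/0.7 = 3.19. With 19 df, power is 94.2% and 85.8%, matching the stated 94% and 85%. Both are for an unadjusted test.

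**2. What a covariate changes.** The unadjusted test is t = ȳ/(s/√n) on n − 1 df. With a covariate centred at its sample mean, the intercept is still ȳ, and t = ȳ/(s_res/√n) on n − 2 df, where s_res² = (1 − r²)s²(n − 1)/(n − 2) and r is the sample correlation. Only the SE and df move.

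**3. How easily noise qualifies at n = 6.** The interval narrows when 2.776·s_res < 2.571·s, that is r² > 1 − (2.571/2.776)²(4/5) = 0.314. For an unrelated covariate this means |t| > 1.354 on 4 df, probability about 0.25. Roughly one noise covariate in four looks helpful.

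**4. Selection, Normal data** (simulation, Visit 8 mean against 0, smallest p among the unadjusted model and K unrelated covariates):

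| K | n = 6, two-sided | n = 6, with negative sign | n = 20, two-sided |
|---|---|---|---|
| 0 | 5.0% | 2.5% | 5.0% |
| 1 | 6.3% | 3.1% | 5.3–5.4% |
| 3 | 8.6% | 4.3% | 5.8–5.9% |
| 5 | 10.4% | 5.2% | 6.1–6.3% |

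Choosing by narrowest CI gave the same n = 6 success-rule rates. A threshold alone helps little: requiring the CI to narrow by at least 20% still gives 6.1, 8.0 and 9.7% two-sided for K = 1, 3 and 5.

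**5. Selection, integer scale, n = 6** (change −1, 0 or +1 with P(nonzero) = SD²; covariate values 2, 3, 4 equally likely; perfect fits not counted as rejections; two-sided):

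| | SD 0.6 | SD 0.7 |
|---|---|---|
| Unadjusted | 1.4% | 3.4% |
| One covariate, fixed in advance | 2.9% | 5.0% |
| Best of 1 / 3 / 5 | 2.9 / 5.5 / 7.6% | 5.0 / 7.8 / 9.9% |

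With one candidate, fixing it in advance gives almost the same rate as choosing it. That rise is therefore lost conservatism of a discrete test, not selection.

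**6. A fixed covariate.** If it is unrelated to change, the Normal-theory rate stays at 5.0%. If it is prognostic, the variance of ȳ over repeated trials is still σ²/n, but the model SE reflects σ²(1 − R²)/n. The rate is 2·P(t₄ > 2.776√(1 − R²)). At R² = 0.15 the cut-off is 2.776 × 0.922 = 2.560, giving 6.3% (simulated 6.2%). At R² = 0.30 it is 2.776 × 0.837 = 2.323, giving 8.1%. This is for the population mean change; conditional on the observed covariate values the rate stays 5%.

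For baseline, R² = (r − k)²/(1 + k² − 2rk), where r is the baseline–follow-up correlation and k = SD(baseline)/SD(follow-up). With r = 0.5 to 0.7, k = 1 gives 0.25 to 0.15, while k = 0.5 to 0.7 gives 0.00 to 0.07. Its effect may be small.

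**7. Which term is tested.** For Visit 8 against Visit 1 under compound symmetry with complete data, the SE comes from the within-subject sum of squares, which is identical with and without a subject-level covariate. Steps 4 to 6 then have no effect. If the term were a raw coefficient with uncentred baseline (grades 2 to 4, slope −0.5 to +0.5, residual SD 0.5), the success rate at zero mean change would run from 0.1% to 22%.

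**8. Part 2, n = 20.** If the protocol's covariate option were used, criterion 1 alone would rise from 2.5% to 3.5% (R² 0.15) or 4.2% (R² 0.25). Criterion 2 needs a mean improvement of at least 0.5: z = 0.5/(0.6/√20) = 3.73, or 0.01%; with SD 0.7, z = 3.19, or 0.07%. That criterion binds first.

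**The case against.** **Little rests on Part 1.** This stands. Protocol 10 and 10.4 reserve the efficacy conclusion for Part 2. Part 2 starts on safety, a mean change near or above 0.5 and feasibility, not on a p-value, and its size uses the SD of Part 1 change scores. A reader might infer that the trial's efficacy claim is inflated; step 8 shows that it is not, materially.

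**The SAP plays down p-values.** Only partly. SAP 8.3 makes the primary analysis inferential and SAP 10.1 decides success by significance.

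**The rate need not rise.** This stands. A reader might infer that any covariate inflates the error. A fixed unrelated covariate keeps 5% under Normal theory, and Visit 8 against Visit 1 under compound symmetry shows no effect. The fallback, which compares baseline with Visit 8, and the phrase about a term coefficient give that contrast some textual support. The tabulated LS means with CIs point the other way. The SAP does not settle it.

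**The choice might be made blind.** A covariate's association with change could be examined in pooled blinded data. The SAP is silent, so unblinded selection is permitted but not shown to be intended.

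**Covariates are not wholly undefined.** Correct: baseline VIIS is named, and only its trigger is open. The unnamed set comes from SAP 8.2.

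**Conclusion.** The concern holds as a gap in pre-specification with a measurable but conditional cost. If the test is the Visit 8 LS mean against 0, or the fallback t-test, choosing helpful covariates at n = 6 can take the two-sided rate from 5% to about 6.3, 8.6 or 10.4% for 1, 3 or 5 unrelated candidates. For the success rule, which also needs a negative sign, that is 2.5% to 3.1, 4.3 or 5.2%. On the integer scale the rate clearly exceeds 5% only with several candidates; with 3 it is 5.5 to 7.8%. A fixed covariate raises the rate for the population mean change only if it is prognostic.

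The sizes rest on assumed numbers of candidates and R², complete data, and one-visit tests rather than the planned unstructured MMRM. The documents do not support saying that the rate always rises, that baseline adjustment is wrong in itself, or that Part 2 is compromised. The consequence is confined to the Part 1 endpoint-met label and its interval. The change is worth making because it costs little.

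**What to change.** - **SAP 8.2:** delete the last paragraph (power-triggered covariates and stratification). State that the sentence treating significance levels as an index of change does not apply to the primary test.
- **SAP 10.1, test:** remove Visit 1 from the visit factor. Define the primary test as the Visit 8 LS mean change from baseline in drug-treated subjects against 0, two-sided 5%.
- **SAP 10.1, baseline:** replace *if useful*, in the model and in the fallback, with a decision fixed before unblinding. Using no covariate is preferable because it matches the unadjusted t-test used for sizing, with one pre-named, centred baseline-adjusted sensitivity model reported whatever its result. Pre-specifying centred baseline as the only covariate is a reasonable alternative and also removes the selection problem.
- **Protocol 10.4 and synopsis:** name in advance any covariate used in the one-sample CI, or state that there is none.

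The cost is wording. Without adjustment the interval may be somewhat wider if baseline is prognostic, and with missing visits the primary model would not use baseline, which the sensitivity model covers. No stated power is lost, because 94% and 85% were calculated without covariates.

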8.3. DATA CONSIDERATIONS

Due to the limited sample size for Part 1 of the clinical trial, descriptive statistics are planned for the primary and secondary endpoints. Inferential statistics will be used for the primary analysis.

8.4. KEY DEFINITIONS AND TERMINOLOGY

Reference start date and study day

Study Day will be calculated from the reference start date and will be used to show start/stop day of assessments and events.

Baseline Value

For purposes of analysis, the baseline value is defined as the last non-missing value obtained prior to initiation of study drug.

Change from Baseline.

Change from baseline for a given endpoint is defined as the difference between a post-treatment study day value and the baseline variable value and will be calculated directionally as post-study minus baseline.

Note that for the VIIS, it is planned that a single investigator will complete this instrument prior to randomization on day 1 of Part 1.

Day 1 (Baseline)

Day 1 is the earliest day that the study drug is first initiated.

Age

Syneos Health #1009367

Age is calculated as the number of whole years from a subject's date of birth to the date of informed consent.

Study Visit.

Study visit is the nominal visit as recorded on the eCRF.

Total Days on Study

Total days on study is defined as the number of days from Day 1 to the date of completion or early termination.

Last Dose of study drug

Last dose of study drug is defined as the number of days from day 1 to the date of last dose of study drug.

Duration of SLS.

The duration of SLS is defined as the number of whole years from the date of onset of SLS diagnosis to the date of informed consent.

Adverse Event

An adverse event is any untoward medical occurrence in a patient or clinical investigation patient, temporally associated with the use of a medicinal product, whether or not considered related to the medicinal product.

Treatment Period

The Treatment Period covers the duration that a patient is in the study from Baseline (Day 1) to Week 24.

Safety Follow-up Period

The Safety Follow-up Period continues for 28 days after the last dose of study treatment at Week 24 through Week 28.

Definition of Study Completion

A patient will be defined as "completed" if she or he completes the Week 24 study visit.

End of Study Definition

Syneos Health #1009367

End of study is defined as the date when the patient has completed one of the following: completed the follow-up visit after the Week 24 visit, permanently discontinued from the study, or lost to follow-up.

Day of Study Termination

Day of study termination = Termination Date - Date of Baseline (Day 1) + 1.

Percent Change from Baseline

Percent CFB = 100 * (Post-baseline value - Value at baseline) / Value at baseline

8.5. MISSING DATA

All available safety, PK and efficacy data will be included in data listings and tabulations. No imputation of missing data is planned for primary and secondary endpoints. Abnormal values for assessments (outliers) will be confirmed during the DRM and the primary analysis may be performed with and without inclusion of outliers.

IMPUTATION OF INCOMPLETE DATES.

An incomplete date is any date for which either the day, month or year is unknown, but all three fields are not unknown. An incomplete date occurs when the exact date an event occurred or ended cannot be obtained from a subject. For many of the analyses, a complete date is necessary in order to determine if the event should be included in the analysis (i.e., if the event is treatment-emergent) or to establish the duration of an event. In such cases, incomplete dates will be imputed.

For purposes of imputation, all events with an incomplete end date are assumed to have ended on or before the day the form was completed. In an effort to minimize bias, the project statistician will impute dates in a systematic, reasonable manner. A list of incomplete and imputed dates will be prepared by the project statistician or statistical programmer(s) and will be submitted for review by the clinical project manager and sponsor.

Syneos Health #1009367

Incomplete/missing start and stop dates will be handled as follows:

Table 8.4.1: Imputation of missing dates

Missing	Imputation
Start day	The start day will be imputed as the first day of the month with the following exception: if the partial date is the same month and year as the date of first dose of double-blind medication, then the partial date will be imputed as the date of first dose of double-blind.
End Day	The end day will be imputed as the last day $(28/29/30/31)$ of the month.
End Day and Month	d The end date will be imputed as the 31st of December or last day of study follow up.

For all other data, all available data will be included in the analyses and will be summarized as far as possible. Unless otherwise specified, there will be no substitution of missing data, i.e., missing data will not be replaced; missing data will be handled as 'missing' in the statistical evaluation.

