11.2. ADVERSE EVENTS / ADVERSE DRUG REACTIONS

Adverse events (AEs) will be coded using a Medical Dictionary for regulatory Activities (MedDRA) version 20.0 or later preferred term (PT) and system organ classification (SOC).

Patients with multiple events within the same System Organ Class and/or same Preferred Term are only counted once within the respective frequencies.

All reported AEs (whether treatment emergent or not) will be included in by-patient AE listings. Sorting will be by patient, date of event, SOC, PT and then verbatim description.

Syneos Health #1009367

An AE will be considered treatment emergent (TEAE) if it begins or worsens in severity after the first dose of the double-blind Study Treatment through 28 days after the last dose of Study Treatment, or the date of initiation of another investigational agent or surgical intervention or rollover to the extension study, whichever occurs first. Partial AE start dates will be imputed as detailed in Section 8.5.

ALL AEs and TEAEs.

Incidence of AE and TEAEs will be presented by SOC and PT. The AE and TEAEs listings will include treatment group, the duration of the event, it severity and whether it was considered to be related to treatment. The listings will also include the number of days between first dose and event.

SOC and PT will be presented, where the severity per patient will be counted at each level of summarization. In addition, a summary of all TEAEs by relationship to Study Treatment (related, not related), SOC and PT will be presented, where the strongest relationship to Study Treatment per patient will be counted at each level of summarization.

SEVERITY.

Severity is classified as mild, moderate, severe or life-threatening.

Missing severity for TEAEs will be counted as 'Severe'.

RELATIONSHIP TO STUY MEDICATION.

Relationship, as indicated by the investigator, will be defined as definitely, possibly, unlikely or not related.

Adverse events with a missing relationship to study medication will be noted as "related" to study medication. If a patient reports the same AE more than once within the same SOC/PT, the AE with the strongest relationship to study medication will be used in the relationship summaries.

TEAEs LEADING TO STUDY DRUG DISCONTINUATION.

TEAEs leading to permanent discontinuation of study medication are those events that are marked as 'discontinued from study' under action taken with study medication in the adverse events page of the CRF.

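### SAP Table 8.4.1 can give an event a start after its own recorded end, and an end after the date its form was completed

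*SAP*

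**What the plan says.** SAP 8.5 explains that incomplete dates are imputed because a full date is needed to decide treatment emergence and to work out duration. The rules are in Table 8.4.1.

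- **Start day missing.** The first of the month is used, except "if the partial date is the same month and year as the date of first dose of double-blind medication". In that case the first-dose date takes its place. Month and year are the only test.
- **End day missing.** "The end day will be imputed as the last day" of the month. No upper limit is given.
- **End day and month missing.** "The end date will be imputed as the 31st of December or last day of study follow up". This is the only row that mentions follow-up, and it does not say which of the two dates applies.

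The text above the table states that "all events with an incomplete end date are assumed to have ended on or before the day the form was completed". A list of incomplete and imputed dates is drawn up and "will be submitted for review by the clinical project manager and sponsor".

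SAP 11.2 relies on these rules: "Partial AE start dates will be imputed as detailed in Section 8.5". It adds no check of start against end. Its TEAE definition requires onset or worsening *after* the first dose. The onset flag in its last listing counts events *on or after* the first dose as on treatment.

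**The concern.** Counting an event as treatment-emergent when the dates cannot settle the matter is a usual and defensible default. The start rule goes further, because it applies the default even when the recorded end date shows that the event was over before dosing. The result is an impossible pair of dates and an on-treatment flag on a pre-treatment event.

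The end rule has a different fault. Section 8.5 states an assumption about when such events ended, and the table then imputes a date that can violate it. Where it does, duration is overstated.

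SAP 11 names incidence, severity and duration of AEs and TEAEs as safety outcomes. Protocol section 10 carries the Part 1 safety data into the Part 2 report. With about nine subjects, a single wrong classification is visible.

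**Working it through.** The documents give no figure on this point, so there is none to reproduce. The check applies Table 8.4.1 as written to calendar dates.

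**Inputs**
- AEs are collected from consent (Protocol 6.5), and Screening is Day -7 to Day -1 (Protocol 7.1). The pre-dose AE window is therefore at most 7 days.
- Arms of about 6 and 3 (Protocol synopsis, statistical analysis).
- Assumptions: first dose equally likely on any of the 365 days of a non-leap year; AE duration = end - start + 1. The SAP gives no AE duration formula, but its exposure formula has this form.

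**1. A worked case for the start rule** (illustrative dates). First dose is 15 August, start day unknown in August, recorded end 10 August.
- Imputed start = 15 August, so duration = 10 - 15 + 1 = -4 days.
- The onset flag reads on treatment, because the start equals the first-dose date.
- If the recorded end is Day -1, duration is 14 - 15 + 1 = 0. Any earlier end makes it negative.

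**2. How often the month test is met, given a missing start day.** A start on Day -k falls in the previous month only if first dose is on one of the first k days of a month, which is 12k dates of 365.
- Share in the first-dose month = 1 - 12k/365.
- k = 1: 353/365 = 96.7%. k = 7: 281/365 = 77.0%.
- Mean over k = 1 to 7 (mean k = 4): 1 - 48/365 = 86.8%.
- Restricted to events that also ended before first dose, with each start/end pair weighted equally, mean k = 140/28 = 5, so 1 - 60/365 = 83.6%. All of these get zero or negative duration.

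These are calendar shares among events that already have a missing start day and a pre-dose onset.

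**3. The end rule.** Suppose the form is completed in the month in which the event ended, on any day with equal chance.
- The imputed end is later than the form date unless the form is completed on the last day of the month: 353/365 = 96.7% of form dates.
- Mean excess past the form date = (7 × 465 + 4 × 435 + 378)/365 = 5373/365 = 14.7 days, where 465, 435 and 378 are L(L-1)/2 for months of 31, 30 and 28 days. The maximum is 30.
- If the form is completed in a later month, the last day of the month agrees with the SAP's assumption. It is then simply the latest date the record allows.

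**4. Effect of one misclassified subject on incidence.** 1/6 = 16.7 percentage points, or 1/3 = 33.3.

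**5. Does the flagged event become a TEAE?** The two boundaries in SAP 11.2 give different answers for a start equal to the first-dose date: no under *after*, taken strictly on dates, and yes under *on or after*. The first-dose default achieves its apparent purpose only under the second. Under the first, an event that truly began after dosing but lacks its start day would drop out of the TEAE tables.

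**The case against.** The strongest reply is that the situation is rare and would be noticed. It needs a missing start day, the first-dose month and an end known to precede first dose, all within a week in which AEs are recorded at Screening and again on Days 1 and 2. The investigator records start and end dates (Protocol 9.1.1.3), and monitors verify all source data (Protocol 12.6). The list of imputed dates is reviewed, listings print missing date parts as dashes (SAP 14.2.5.3), and no inferential safety testing is planned (SAP 11). The statement about form completion could also be read as an implied cap on the table.

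Most of this stands as a limit on size. It does not remove the fault: the review step has no override rule, so any correction would be ad hoc, and a programmer working from the table would find no cap in the End Day row.

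A reader might infer more than the documents support:
- *Pre-treatment events in general become treatment-emergent.* A start in an earlier month goes to the first of that month and stays pre-treatment.
- *Durations generally run too long.* This fits only the end rule, which conflicts with the stated assumption only when the form predates month-end. For a pre-dose event, the start rule shortens duration or makes it negative.
- *About 87% of screening events are misclassified.* That figure is conditional on a missing start day, and the documents do not say how many there are.
- *A medicine stopped before dosing becomes concomitant.* SAP 9.6.2 requires it to be ongoing at or after first dose or newly started after it, so a stopped medicine does not qualify.

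**Conclusion.** The point holds in a narrow form. The start rule can give an event a start after its recorded end and flag it as on treatment. Whether it is also counted as a TEAE depends on which boundary in SAP 11.2 is programmed. The uncapped End Day row contradicts the SAP's own assumption when the form is completed before the end of the month. The 14.7-day mean excess rests on same-month, evenly spread form completion. It measures distance past the form date, not past the true end. Visits after Day 2 are about four weeks apart, so many forms may be completed in a later month, where no conflict arises.

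This is a minor correction. Few events are likely to be involved and efficacy is untouched. It is still worth making because these are stated rules that yield wrong dates, and one subject is a sixth or a third of an arm.

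**What to change.** Make three changes to the SAP.

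1. **Start rule, Table 8.4.1.** Use the first-dose date only if the end date is missing, or is or could be on or after first dose. Otherwise classify the event as pre-treatment and, for AEs, impute the start as the later of the first of the month and the consent date, never after the recorded end. The consent bound matters. In the worked case with consent on 8 August, the first of the month would give 10 - 1 + 1 = 10 days and a start before AE collection began, whereas the bounded rule gives 10 - 8 + 1 = 3 days.
2. **End rule, Table 8.4.1.** Impute a missing end day as the earliest of the last day of the month, the form completion date and the last study contact. Apply this before the start rule, so that a form completed before first dose also settles emergence.
3. **SAP 11.2.** Use one boundary, either *after* or *on or after* first dose, in both the TEAE definition and the onset flag.

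The cost is a few phrases in the SAP and minor re-programming.
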